### **Drug and Alcohol Screen**

At screening and End of Treatment/Early Termination visit, a urine drug screen and alcohol test will be performed.

### **Pregnancy Testing**

Urine pregnancy tests will be performed on females of childbearing potential at Screening (Visit 1) and End of Treatment/Early Termination visit (Visit 4). Negative results are required for trial admission and/or administration of IMP.

## **8 ADVERSE EVENTS**

### **8.1 Adverse Event Definition**

An adverse event is any untoward medical occurrence in a subject participating in a clinical trial. It includes:

- Any unfavorable and unintended sign, symptom or disease temporally associated with the use of the IMP, whether or not considered to be caused by the IMP.
- Adverse events commonly observed and adverse events anticipated based on the pharmacological effect of the IMP.
- Any laboratory abnormality, vital sign or finding from physical (or gynecological) examination assessed as clinically significant by the investigator (note: findings from assessments and examinations done during screening are not adverse events, but are recorded as medical history).
- Accidental injuries, reasons for any change in medication (drug and/or dose), reasons for any medical, nursing or pharmacy consultation, or reasons for admission to hospital or surgical procedures.
- Overdoses and medication errors with and without clinical consequences.

An adverse drug reaction is an adverse event evaluated by the investigator as being probably or possibly causally related to treatment with the IMP.

A serious adverse drug reaction is a serious adverse event (SAE) evaluated by the investigator and/or by Ferring as having a reasonable possibility of causal association with IMP.

An unexpected adverse event is an adverse event not identified in nature, severity, or frequency in the section “Undesirable Effects” in the sponsor’s current Investigator’s Brochure.

A treatment-emergent adverse event is any adverse event that begins during the Treatment Period or worsening of a pre-existing medical condition. The Treatment Period is the period during which a subject receives IMP.

### **8.2 Collection and Recording of Adverse Events**

#### **8.2.1 Collection of Adverse Events**

The investigator must monitor the condition of the subject throughout the trial from the time of obtaining informed consent until the Day 19 follow-up phone call.

The sources of adverse events cover:

- The subject's response to questions about his/her health (a standard non-leading question such as "How have you been feeling since your last visit?" is asked at each visit).
- Symptoms spontaneously reported by the subject.
- Investigations and examinations where the findings are assessed by the investigator to be clinically significant changes or abnormalities.
- Other information relating to the subject's health becoming known to the investigator (e.g., hospitalization).

### **8.2.2 Recording of Adverse Events**

The investigator must record all adverse events in the Adverse Event Log provided in each subject's eCRF with information about:

- Adverse event
- Date and time of onset (time can be omitted, if applicable)
- Intensity
- Causal relationship to IMP
- Action taken to IMP
- Other action taken
- Date and time of outcome (time can be omitted, if applicable)
- Outcome
- Seriousness

Each of the items in the Adverse Event Log is described in detail in the following sections.

#### **Adverse Event**

Adverse events should be recorded as diagnoses, if available. If not, separate signs and symptoms should be recorded. One diagnosis/symptom should be entered per record.

If a subject suffers from the same adverse event more than once and the subject recovers in between the events, the adverse events should be recorded separately. If an adverse event changes in intensity, a

worst-case approach should be used when recording the event, i.e. the highest intensity and the longest duration of the event.a

Pre-existing conditions are not AEs, but become AEs if worsening occurs after IMP administration during the trial. Pre-existing clinically significant conditions diagnosed or observed as a result of the screening procedures must be recorded as medical history.

Note: A procedure is not an adverse event; the reason for conducting the procedure is. Hospitalization is not an adverse event; the reason for hospitalization is. Death is not an adverse event, but the cause of death is (an exception is sudden death of unknown cause, which is an adverse event).

### **Date and Time of Onset**

The date of onset is the date when the first sign(s) or symptom(s) were first noted. If the adverse event is an abnormal clinically significant laboratory test or outcome of an examination, the onset date is the date the sample was taken or the examination was performed.

### **Intensity**

The intensity of an adverse event must be classified using the following 3-point scale:

Mild: Awareness of signs or symptoms, but no disruption of usual activity.

Moderate: Event sufficient to affect usual activity (disturbing).

Severe: Inability to work or perform usual activities (unacceptable).

---

a Exception: if an adverse event with onset before the first IMP administration (i.e., a pre-treatment adverse event) changes in intensity, this must be recorded as 2 separate events. The initial adverse event should be recorded with outcome “not yet recovered” and the date and time of outcome is when the intensity changed. The second adverse event should be recorded with date and time of onset when the intensity changed.

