### 10.2 Adverse Events

Adverse events (AEs) are classified according to the MedDRA version 16.1 give a system organ class and preferred term for each event.

A treatment-emergent adverse event (TEAE) is any adverse event that begins during the treatment period or worsening of a pre-existing medical condition. The Treatment Period is the period during which a subject receives IMP (including the residual time of drug effect). More specifically, for subjects who completing all doses as planned on Day 14, the Treatment Period is Day 1 to Day 15. For subjects who discontinued IMP, the Treatment Period is Day 1 to the dose date + 1.

TEAEs will be listed by treatment and subject, and the incidence of TEAEs will be presented by treatment. In addition, TEAEs will be presented by causality (relationship to the trial medication) and intensity (severity) and seriousness. Serious adverse events (SAEs) and adverse events leading to discontinuation will be listed.

If a subject has an AE with unknown intensity, then the subject is counted in the category of “Severe”. If an AE with unknown relationship to IMP, then the AE is considered to be related to IMP.

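### As written, the split-record rule for pre-treatment adverse events, read with the TEAE definition, could tabulate an on-treatment improvement as a treatment-emergent event

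*Combined protocol and SAP*

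**What the plan says.** The general rule in protocol 8.2.2 (Adverse Event) is that an event whose intensity changes stays as one record, kept at its worst grade and longest duration. Footnote a, under Intensity, makes an exception for events that start before the first dose. If such an event "changes in intensity, this must be recorded as 2 separate events", the first record is closed as not yet recovered at the time of the change, and "The second adverse event should be recorded with date and time of onset when the intensity changed".

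Protocol 8.1 defines a TEAE as "any adverse event that begins during the Treatment Period or worsening of a pre-existing medical condition". SAP 10.2 repeats the definition almost word for word ("any adverse event that begins during the treatment period or worsening of a pre-existing medical condition") and sets the window: "for subjects who completing all doses as planned on Day 14, the Treatment Period is Day 1 to Day 15". For subjects who discontinue, it closes at the dose date plus 1.

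Protocol 8.2.1 collects events "from the time of obtaining informed consent until the Day 19 follow-up phone call", so an event can start before dosing and continue into treatment. SAP 10.2.1 and 10.2.2 tabulate TEAEs in an overview and by system organ class and preferred term, causality and intensity. One table is limited to terms reaching 5% of subjects in any treatment group.

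**The concern.** The split serves a purpose when an event worsens after dosing, because the worsening then has its own on-treatment onset. But the footnote is triggered by any change. The TEAE definition has two alternative limbs, and only the second mentions worsening. The first asks only when the record begins. A pre-treatment event that eases on treatment thus produces a record that the first limb accepts.

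Safety and tolerability is a named secondary objective, and these tables are the main between-arm display for it. An improvement shown there as a new event says the opposite of what happened. It also receives its own causality rating, and SAP 10.2 treats an unknown relationship as related.

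**Working it through.** The plan states no figure to reproduce; this is a classification rule. The check applies the text literally and then sizes one record.

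**Step 1. Does the footnote cover a fall in intensity?** It states no direction. The general rule it modifies uses the same trigger, a change in intensity, and resolves it by keeping the highest grade, which covers rises and falls alike. Where section 8.2.2 means worsening only, it says so, but that sentence concerns pre-existing conditions, not pre-treatment adverse events.

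**Step 2. Does the second record meet the TEAE definition?** Take an event with onset on Day -3 in a subject who completes dosing (window Day 1 to Day 15):

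| Change | Onset of second record | TEAE as written |
|---|---|---|
| Severe to mild on Day 5 | Day 5 | Yes |
| Mild to severe on Day 5 | Day 5 | Yes |
| Severe to mild on Day -1 | Day -1 | No |
| Severe to mild on Day 17 | Day 17 | No |

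The first row is the defect. The second is the case the split is useful for.

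**Step 3. Does anything later remove it?** SAP 10.2 to 10.2.2 contain no rule that links the second record to the first, compares their grades, or excludes a lower grade.

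**Step 4. What can one record do to a table?** Planned arm size is 19 (protocol 9.1, SAP 3.2). One subject is 1/19 = 5.3% of the arm, above the 5% threshold in SAP 10.2.2. The same holds for any arm of 20 or fewer (1/20 = 5.0%); with 21 it fails (1/21 = 4.8%). Incidence counts subjects, so the percentage moves only if the subject has no other TEAE under that preferred term. Otherwise only the event count rises, by one.

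**Step 5. How many events could qualify?** All of the following must hold:

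- a new event starts after consent and before the first dose;
- it is neither a screening finding nor a pre-existing condition, since both go to medical history (protocol 8.1, 8.2.2);
- it persists into dosing;
- it drops at least one grade on the three-point scale within the window without resolving, because recovery is recorded as an outcome, not as an intensity change.

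The documents give no adverse event rates, so the count cannot be estimated. The pre-dose interval is not fixed either: protocol 6.1.1 allows consent before the Screening Visit.

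**The case against.** The strongest case against is that the effect is rare and has little consequence. The chain in Step 5 is long. Safety is descriptive, with no formal testing (protocol 9.8.1, SAP 10.1). The rule is the same in both blinded arms, and pre-dose events precede any drug effect, so the main result is noise. The investigator can rate an improving pre-dose event as having no reasonable possibility of a causal link, which keeps it out of the adverse drug reactions. The second record carries the lower grade, so it cannot appear as severe unless its intensity is unknown. All adverse events are listed, and the first record is closed as not yet recovered, so a reader can trace the pair. The worsening limb also suggests that only worsening was meant to count. All of this stands and limits the weight of the point. It does not correct the rule: the footnote is mandatory, and programming from onset dates would flag the record.

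A reader might infer that the tables are certain to contain improvements, or that the comparison will be biased against carbetocin. The documents support neither. Whether any event qualifies is unknown, and no reason is given why pre-dose events should differ systematically by arm. If the drug itself eased symptoms, improvements could differ by arm, but the documents provide nothing with which to size that.

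**Conclusion.** The point holds in a limited form. Under the written rules, a pre-treatment adverse event that steps down in grade within the Treatment Period could be tabulated as a TEAE, and nothing in the SAP takes it out. This is a wrong result from a stated rule, not a missing detail.

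The size is one event per occurrence, plus 5.3 percentage points on a preferred-term line when the subject has no other TEAE under that term. This assumes the planned 19 per arm and a literal reading of the footnote and the first TEAE limb. The number of occurrences is probably small and cannot be estimated from the documents. The primary analysis is unaffected. It is a minor correction, worth making because it costs so little.

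**What to change.** Keep the Treatment Period window and the limb on worsening of a pre-existing medical condition as they are. Add one sentence to SAP 10.2, and the same sentence to protocol 8.1 so that the two definitions still agree:

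*A second record created by splitting a pre-treatment AE under protocol 8.2.2 footnote a counts as a TEAE only if its intensity exceeds the pre-dose intensity of the original event.*

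Under this rule severe to mild on Day 5 gives no TEAE instead of one, and mild to severe on Day 5 still gives one. Redefining a TEAE as any event with first onset after the first dose would be a worse repair: it would remove the end of the window, drawing in events reported up to the follow-up call, and could lose worsening of medical-history conditions.

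The alternative is to limit footnote a to increases in intensity, so that improvements return to the single worst-case record. That changes data collection and the eCRF guidance.

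The added sentence leaves data collection unchanged. It needs a short programming step to pair the records, which the footnote makes possible because the first record's outcome time is the second record's onset time. It should be settled before unblinding.

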## **Causal Relationship to IMP**

The possibility of whether the IMP caused the adverse event must be classified as one of the following:

Reasonable possibility:

There is evidence or argument to suggest a causal relationship between the IMP and the adverse event. The adverse event may occur as part of the pharmacological action of the IMP or may be unpredictable in its occurrence.

Examples:

- Adverse events that are uncommon but are known to be strongly associated with IMP exposure.
- Adverse events that are not commonly associated with IMP exposure, but the event occurs in association with other factors strongly suggesting causation, such as a strong temporal association or the event recurs on rechallenge.

No reasonable possibility:

There is no reasonable evidence or argument to suggest a causal relationship between the IMP and the adverse event.

Examples:

- Known consequences of the underlying disease or condition under investigation.
- Adverse events common in the trial population, which are also anticipated to occur with some frequency during the course of the trial, regardless of IMP exposure.

## **Action Taken to IMP**

The action taken to the IMP in response to an adverse event must be classified as one of the following:

- No change (medication schedule maintained or no action taken)
- Withdrawn
- Interrupted
- Dose reduced
- Dose increased

## **Other Action Taken**

Adverse events requiring therapy must be treated with recognized standards of medical care to protect the health and well-being of the subject. Appropriate resuscitation equipment and medicines must be available to ensure the best possible treatment of an emergency situation.

If medication is administered to treat the adverse event, this medication should be entered in the Concomitant Medication Log.

## **Date and Time of Outcome**

The date the subject recovered or died.

## **Outcome**

The outcome of an adverse event must be classified as one of the following:

- Recovered (fully recovered or the condition has returned to the level observed at initiation of trial treatment)
- Recovered with sequelae (resulted in persistent or significant disability/incapacity)
- Recovering
- Not yet recovered
- Fatal

### **8.3      Pregnancy and Pregnancy Outcome**

If a pregnancy occurs, the IMP should be immediately stopped and Pharmacovigilance at Ferring Pharmaceuticals must be informed and a SAE form completed. The mother and the fetus must be followed at least until the birth of the infant and 1 month after the birth of the infant. In general, the follow-up will include the course, duration, and the outcome of the pregnancy, as well as neonatal health. If a pregnancy results in an abnormal outcome (birth defect/congenital anomaly), this must be reported as an SAE to Pharmacovigilance at Ferring Pharmaceuticals.

In cases in which a fetus may have been exposed through transmission of the IMP via semen following paternal exposure and the pregnancy results in an abnormal outcome (birth defect/congenital anomaly), this must be reported as a serious adverse event to Pharmacovigilance at Ferring Pharmaceuticals.

## 8.4 Serious Adverse Events

### 8.4.1 Serious Adverse Event Definition

#### Serious Adverse Events during the Trial

An event is defined a serious adverse event if it:	Guidance
results in death	Any event resulting in a fatal outcome must be fully documented and reported, including deaths occurring within 4 weeks after the treatment ends and irrespective of the causal relationship to the IMP. The death of a subject enrolled in a trial is per se not an event, but an outcome.
is life-threatening	The term life-threatening refers to an adverse event in which the subject was at immediate risk of death at the time of the event. It does not refer to an event, which may have caused death if it were more severe.
requires in-patient hospitalization or prolongation of existing hospitalization	The term hospitalization means that the subject was admitted to hospital or that existing hospitalization was extended as a result of an event. Hospitalization describes a period of at least 24 hours. Over-night stay for observation, stay at emergency room or treatment on an out-patient basis do not constitute a hospitalization. However, medical judgment must always be exercised and when in doubt the case should be considered serious (i.e. if case fulfills the criterion for a medically important event). Hospitalizations for administrative or social purposes do not constitute a serious adverse event (SAE). Hospital admissions and/or surgical operations planned before trial inclusion are not considered adverse events, if the illness or disease existed before the subject was enrolled in the trial, provided that the condition did not deteriorate during the trial.
results in persistent or significant disability/incapacity	Disability/incapacity means a substantial disruption of a person's ability to conduct normal life functions. In doubt, the decision should be left to medical judgment by the investigator.
is a congenital anomaly/birth defect	Congenital anomaly/birth defect observed in any offspring of the subject conceived during treatment with the IMP.
is an important medical event	Important medical events are events that may not be immediately life-threatening or result in death or hospitalization but may jeopardize the subject or may require intervention to prevent one of the other outcomes listed in the definition above. Examples of important medical events include adverse events that suggest a significant hazard, contraindication or precaution, occurrence of malignancy or development of drug dependency or drug abuse. Medical and scientific judgment should be exercised in deciding whether events qualify as medically important.  Important medical events include any suspected transmission of an infectious agent via a medicinal product. Any organism virus or infectious particle (e.g. prion protein transmitting Transmissible Spongiform Encephalopathy), pathogenic or non-pathogenic, is considered an infectious agent. A transmission of an infectious agent may be suspected from clinical symptoms or laboratory findings indicating an infection in a subject exposed to a medicinal product.

#### **8.4.2 Collection, Recording and Reporting of Serious Adverse Events**

##### **SAE Reporting by the Investigator**

All SAEs must be reported **immediately** to Ferring Pharmacovigilance as soon as it becomes known to the investigator and not later than within 24 hours of their knowledge of the occurrence of an SAE.

The investigator is responsible for submitting the completed SAE Report Form with the fullest possible details **within 24 hours** of his/her knowledge of the SAE.

The SAE Report Form must be completed and submitted according to the instructions provided on the form, using the contact details below:

Pharmacovigilance, Ferring Pharmaceuticals Inc.  
[contact]

Email: [contact]

Completion of the Demographics, Adverse Event Log, Medical History Log and Concomitant Medication Log are mandatory for initial reports and for follow-up reports if any relevant changes have been made since the initial report.

Additional information relevant to the SAE such as hospital records, results from investigations, e.g., laboratory parameters, invasive procedures, scans and x-rays, and autopsy results can be faxed or scanned and e-mailed to Ferring Pharmacovigilance using the contact details in the section above. In any case this information must be supplied by the investigator upon request from Ferring. On any copies provided, such details such as subject's name, address, and hospital ID number should be concealed and instead subject number should be provided.

The investigator will supply Ferring and the IRB with any additional requested information such as results of post-mortem examinations and hospital records.

## **Expedited Reporting by Ferring**

Ferring will report all adverse events that are **serious, unexpected (according to the Investigator Brochure) and with a reasonable possible causality to the IMP** as judged by either the investigator or Ferring to the relevant parties within the stipulated timelines. Ferring will submit serious, unexpected, causally-related adverse event reports to the US Food and Drug Administration and other applicable Health Authorities according to local reporting requirements.

Serious adverse events will be considered reportable regardless of whether or not the IMP was used in accordance with the provisions in the protocol, Investigator's Brochure and labeling.

### **8.5 Follow-up of Adverse Events and Serious Adverse Events**

#### **8.5.1 Follow-up of Adverse Events with Onset during the Trial**

During the trial, the investigator must follow-up on each adverse event until it is resolved or until the medical condition of the subject is stable.

After the subject's last visit, the investigator must follow-up on any adverse event classified as serious or considered to have a reasonable possible causality to the IMP until it is resolved or until the medical condition of the subject is stable. All such relevant follow-up information must be reported to Ferring. If the event is a chronic condition, the investigator and Ferring may agree that further follow-up is not required.

